#### Efficacy Analyses

All efficacy analyses will be based on the MITT, as well as the PP analyses set.

Endpoints will be summarized by treatment sequence depending on the treatment received in Study ADS-AMT-MS301:

Sequence No.	Study ADS-AMT-MS301 Treatment	Study ADS-AMT-MS303 Treatment
1	Placebo	274 mg/d ADS-5102
2	137 mg/d ADS-5102	274 mg/d ADS-5102
3	274 mg/d ADS-5102	274 mg/d ADS-5102

Efficacy results will be analyzed by treatment sequences 1, 2, and 3 shown above and also by sequences 2 and 3 combined (ie, treatment sequence 1 versus 2 and 3 combined). Descriptive statistics (ie, mean, standard error, median, minimum/maximum, 95% confidence intervals [CI] for the changes from baseline) for each parameter at each study visit will be generated. Missing data will not be imputed. Graphical depictions of changes over time will be provided.

The proportion of Novel Responders in walking speed for each treatment sequence as well as pooled sequences 2 and 3 will also be characterized. The counts and percentages of Novel Responders, Non-Responders and discontinuations at each study visit will be presented.

For parameters measured on a continuum (eg, MSWS-12, T25FW (ft/sec)), the treatment-sequence time trend will be explored using a Mixed Model Repeated Measures (MMRM) model with the change from baseline as the dependent variable, fixed effects of treatment-sequence, study visit (ie week 12, 24 and 52), treatment-sequence by study visit interaction, baseline value as a covariate and an unstructured variance-covariance matrix for the within-subject residual variability. Appropriate contrasts comparing specific weeks between treatment-sequences will be derived from this model. For the proportion responders, a GEE (generalized estimating equation) model for a binomial variate will be used.

Details of all analyses will be provided in the statistical analysis plan (SAP) for this study.

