## 5. INTRODUCTION

This is an open-label extension (OLE) study for subjects who complete 16 weeks of study drug treatment and a Week 16 visit in Study ADS-AMT-MS301, “A 3-Arm, Multicenter, Double-Blind, Placebo-Controlled, Randomized Study to Assess the Efficacy and Safety of ADS-5102 Amantadine Extended Release Capsules in Multiple Sclerosis Patients with Walking Impairment.” The primary purpose of this study is to extend the evaluation of the safety and tolerability of ADS-5102, an extended-release (ER) capsule formulation of amantadine administered at 274 mg/d, in subjects with multiple sclerosis (MS) and walking impairment from 12 weeks, as in Study ADS-AMT-MS301, to 52 weeks or 64 weeks (including the duration of ADS-AMT-MS301). Additionally, this study is intended to provide supportive evidence of the efficacy of ADS-5102 as a treatment for walking impairment in MS (by way of treating the former ADS-AMT-MS301 placebo subjects), as well as an assessment of the durability of efficacy up to 64 weeks.

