### **6.2. Secondary Objectives**

- To characterize the efficacy of ADS-5102 in subjects with MS and walking impairment as measured by the T25FW (feet/second) at Week 52.
- To characterize the efficacy of ADS-5102 in subjects with MS and walking impairment as measured by the Timed Up and Go (TUG) test, the 2 Minute Walk Test (2MWT), and the Multiple Sclerosis Walking Scale-12 (MSWS-12) at Week 52.
- To characterize the efficacy of ADS-5102 in subjects with MS and walking impairment as measured by the T25FW, the TUG test, the 2MWT, and the MSWS-12 at Weeks 12 and 24, and across all three time points (Weeks 12, 24 and 52).

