## 14.5. Efficacy Analyses

All efficacy analyses will be based on the MITT, as well as the PP analyses set.

Endpoints will be summarized by treatment sequence depending on the treatment received in [Study ADS-AMT-MS301](#):

Sequence No.	Study ADS-AMT-MS301 Treatment	Study ADS-AMT-MS303 Treatment
1	Placebo	274 mg/d ADS-5102
2	137 mg/d ADS-5102	274 mg/d ADS-5102
3	274 mg/d ADS-5102	274 mg/d ADS-5102

Efficacy results will be analyzed by treatment sequences 1, 2, and 3 shown above and also by sequences 2 and 3 combined (ie, treatment sequence 1 versus 2 and 3 combined). Descriptive statistics (ie, mean, standard error, median, minimum/maximum, 95% confidence intervals [CI] for the changes from baseline) for each parameter at each study visit will be generated. Missing data will not be imputed. Graphical depictions of changes over time will be provided.

The proportion of Novel Responders in walking speed for each treatment sequence as well as pooled sequences 2 and 3 will also be characterized. The counts and percentages of Novel Responders, Non-Responders, and discontinuations at each study visit will be presented.

For parameters measured on a continuum (eg, MSWS-12, T25FW (ft/sec)), the treatment-sequence time trend will be explored using an MMRM model with the change from baseline as the dependent variable, fixed effects of treatment-sequence, study visit (ie week 12, 24 and 52), treatment-sequence by study visit interaction, baseline value as a covariate and an unstructured variance-covariance matrix for the within-subject residual variability. Appropriate contrasts comparing time trends between treatment-sequences will be derived from this model. For the proportion responders, a GEE (generalized estimating equation) model for a binomial variate will be used.

Details of all analyses will be provided in the statistical analysis plan (SAP) for this study.

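### The synopsis and Section 14.5 name different between-sequence contrasts for the same MMRM; the time-trend contrast in 14.5 is zero under an early, sustained gain, and neither names a three-visit average.

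*Combined protocol and SAP*

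**What the plan says.** Section 14.5 and the synopsis (Efficacy Analyses) describe one model for the continuous endpoints. Section 14.5 calls it an "MMRM model with the change from baseline as the dependent variable", with "fixed effects of treatment-sequence, study visit (ie week 12, 24 and 52), treatment-sequence by study visit interaction, baseline value as a covariate" and an unstructured covariance matrix. Its stated purpose is exploratory: "the treatment-sequence time trend will be explored using an MMRM model".

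The two passages then differ on what is taken from the model:

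- Section 14.5: "Appropriate contrasts comparing time trends between treatment-sequences will be derived from this model".
- Synopsis: "Appropriate contrasts comparing specific weeks between treatment-sequences will be derived from this model".

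The secondary objectives in Section 6.2 ask for efficacy "as measured by the T25FW (feet/second) at Week 52", for the other three measures at Week 52, and for all four measures "at Weeks 12 and 24, and across all three time points (Weeks 12, 24 and 52"). Section 5 expects supportive efficacy evidence "by way of treating the former ADS-AMT-MS301 placebo subjects", together with an assessment of durability.

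Both analysis passages also plan by-visit descriptive statistics per sequence with 95% confidence intervals, a comparison of sequence 1 with sequences 2 and 3 pooled, and a GEE model for responders. Both leave further detail to the SAP.

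**The concern.** A contrast at a given week and a contrast of time trends answer different questions. The first asks whether the sequences differ in change from Week 0 at that visit. The second asks whether that difference alters between visits. Week 0 is not a level of the visit factor, and all three modelled visits come well after the two-week titration. A trend contrast therefore compares the course from Week 12 to Week 52 and carries no information about a gain already complete at Week 12. That gain is what Section 5 wants to see in former placebo subjects.

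Two things are at stake. An analyst following 14.5 alone could report a null between-sequence contrast when the former placebo subjects had improved and stayed improved. And the named trend contrast estimates none of the effects in the secondary objectives: Week 52, Weeks 12 and 24, or the three visits together.

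**Working it through.** The plan gives no effect size, SD, power or alpha for efficacy, so there is no figure of its own to reproduce. The 540 in Section 14.1 is a roll-over ceiling.

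**Step 1: algebra on the model's cell means.** Let d12, d24 and d52 be the differences in mean change from Week 0, sequence 1 minus a comparator.

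- Week-specific contrasts: d12, d24, d52.
- Three-visit average: (d12 + d24 + d52)/3.
- Trend as Week 52 minus Week 12: d52 − d12.
- Trend as linear slope: the mean of 12, 24 and 52 is 88/3 = 29.33, so the centred weights are −17.33, −5.33 and +22.67 (exactly −52/3, −16/3, 68/3), which sum to 0.
- Trend as the two-degree-of-freedom sequence-by-visit interaction: tests d12 = d24 = d52.

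Every form of trend has visit weights that sum to zero. With d12 = d24 = d52 = g, each trend contrast is g × 0 = 0 for any g, while each week-specific contrast and the average equal g. The baseline covariate has one slope common to all visits, so it also cancels from the trend.

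**Step 2: how far the zero depends on the pattern.** Assumed gain 0.20 ft/s, before baseline adjustment:

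| Pattern | d12 | d24 | d52 | Average | W52 − W12 | Slope per 52 weeks |
|---|---|---|---|---|---|---|
| Sequence 1 gains by Week 12 and keeps it; comparators flat | 0.20 | 0.20 | 0.20 | 0.20 | 0 | 0 |
| Same, all decline in parallel by 0.10 | 0.20 | 0.20 | 0.20 | 0.20 | 0 | 0 |
| Sequence 1 keeps the gain; comparators decline by 0.10 | 0.20 | 0.23 | 0.30 | 0.243 | 0.10 | 0.13 |
| Gain still building | 0.10 | 0.15 | 0.20 | 0.15 | 0.10 | 0.123 |

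The zero holds in the first two rows only.

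**Step 3: illustration with the planned baseline adjustment, sequence 1 minus sequence 3.** Assumptions, none from the documents: 180 per sequence (540 split equally), effect 0.20 ft/s by Week 12 and kept, between-subject SD 0.6, measurement SD 0.25, random-walk drift SD 0.15 per visit, no dropout. Sequence 3 has already been on 274 mg/d in the parent study, so under these assumptions its Week 0 mean is 0.20 higher.

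- Baseline variance: 0.36 + 0.0625 = 0.4225. Covariance of change with baseline: −0.0625. Slope: −0.0625/0.4225 = −0.148.
- Adjusted difference: 0.20 − 0.148 × 0.20 = 0.170, at each visit and for the average.
- Variance removed by the covariate: 0.0625²/0.4225 = 0.0092.
- Week 52: variance 2 × 0.0625 + 3 × 0.0225 − 0.0092 = 0.1833; SE = √(2 × 0.1833/180) = 0.045; z = 0.170/0.045 = 3.8.
- Three-visit average: variance 0.0625 + 0.0625/3 + (14/9) × 0.0225 − 0.0092 = 0.1091; SE = √(2 × 0.1091/180) = 0.035; z = 0.170/0.035 = 4.9.
- Trend (Week 52 minus Week 12): variance 2 × 0.0625 + 2 × 0.0225 = 0.17; SE = √(2 × 0.17/180) = 0.043; expected value 0.

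Simulation under the same settings agrees: 0.170 (SD 0.045) at Week 52, 0.171 (SD 0.035) for the average, and 0.001 (SD 0.043) for the trend.

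**The case against.** The case on the other side is substantial.

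- A reader might infer that 14.5 restricts the analysis to trend contrasts. It does not. It names no other contrast but excludes none, and the synopsis is part of the same protocol.
- A reader might infer that the MMRM is the only model comparing sequences. The responder GEE is also planned, and an early gain could show there at every visit, though its contrasts are unspecified.
- A reader might infer that the model cannot deliver the across-visit effect. It can. With a sequence-by-visit interaction and sum-to-zero coding, the sequence main effect is the equally weighted average over the three visits. The objective's wording could also be read as the course over time.
- The efficacy objectives are to characterise, without a stated hypothesis test. By-visit means with 95% confidence intervals would show a sustained gain in the former placebo group. The primary objective is safety, and a trend contrast suits the durability aim.
- Details are left to the SAP.

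All of this limits the consequence; it does not remove the conflict. The by-visit summaries describe each sequence separately, on observed data and without baseline adjustment, so they are not between-sequence contrasts. Leaving detail to a SAP does not say which of two current, incompatible statements governs, and the combined document contains no separate SAP text that settles it. If time trend was meant to include the rise from Week 0, the model as written does not express that, because Week 0 is not a visit level.

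**Conclusion.** The inconsistency is real and lies in the specification, not in the model. The contrast named in 14.5 is exactly zero, whatever the size of the gain, if former placebo subjects gain by Week 12 and keep the gain while sequences 2 and 3 run flat or parallel. In that case it cannot show the supportive efficacy described in Section 5. It is non-zero if the comparators drift or the gain is still building.

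The 0.17 ft/s and the z values of about 3.8 and 4.9, against 0 for the trend, rest on assumed effect, variances, split and no dropout, and are illustrative only. Leaving out the baseline covariate would give 0.20 ft/s, but that is not the planned analysis. The zero needs none of these values, only the flat-or-parallel pattern.

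The documents do not support concluding that the efficacy objectives have no analysis or that a sustained gain would go unseen. The narrower conclusion is that the between-sequence contrasts are specified inconsistently and that no contrast is named for the three time points together.

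**What to change.** Use one identical sentence or list in the synopsis and Section 14.5, and carry it into the SAP:

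1. LS mean change with 95% CI per sequence at Weeks 12, 24 and 52, and sequence contrasts at each of these weeks, including sequence 1 versus 2 and 3 combined.
2. The equally weighted average over the three visits per sequence, with the same contrasts, as the analysis for the third secondary objective.
3. The Week 52 minus Week 12 trend contrast, labelled as a separate durability question.

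The cost is a short text change and a few extra contrast statements on a model already planned. No new data, visits or model are needed.

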## 14.6. Safety and Tolerability Analyses

All safety analyses will be based on the Safety analysis set. Adverse events in Study ADS-AMT-MS303 will be recorded starting immediately following completion of the last study procedure for [Study ADS-AMT-MS301](#) at a Week 16 Visit for that study (which also serves as the first visit for Study ADS-AMT-MS303). All AEs will be listed by subject and period of onset: pre-dose and TEAEs.

The incidence of TEAEs will be summarized by treatment sequences 1, 2, and 3, and overall for all subjects. The incidence of the following will be presented by system organ class (SOC) and preferred term (PT) within SOC in the safety analysis set.

- TEAEs
- Investigator-determined treatment-related TEAEs
- TEAEs leading to drug discontinuation
- TEAEs by severity

- Serious TEAEs (STEAEs)
- Investigator-determined treatment-related STEAEs
- Discontinuation due to STEAEs

Clinical laboratory test parameters will be listed for individual subjects and values outside of the reference ranges will be flagged. The incidence of potentially clinically significant changes in laboratory parameters at each study visit will be tabulated. Vital signs measurements at each timepoint will be listed by subject. The incidence of potentially clinically significant changes at each study visit will be summarized.

Descriptive statistics for the mean and mean changes in the C-SSRS will be generated by study visit. Results will also be graphically depicted.

Descriptive statistics for the mean and mean change from ADS-AMT-MS301 Screening value in the EDSS will be generated.

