### 11.3. Columbia-Suicide Severity Rating Scale (C-SSRS)

The C-SSRS will be performed at every visit. Full details on how this assessment is to be performed will be provided in the study manual.

While the C-SSRS can provide valuable information as to the presence and intensity of suicidal ideation, determining the need for, and appropriate level of, therapeutic intervention depends on clinical judgment. The Joint Commission has published guidelines for treating suicidal ideation, “Sentinel Event Alert 56: Detecting and treating suicide ideation in all settings,” along with other resources that may prove useful to the investigator, available at: [https://www.jointcommission.org/sea\\_issue\\_56/](https://www.jointcommission.org/sea_issue_56/).

Subjects should also be monitored for depression, depressed mood, confusional state, and/or apathy, as well as suicidal ideation or behavior. New or worsening depression should be captured as an adverse event and treated appropriately per the Investigator's obligation and judgement.

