## 12. EVALUATIONS BY VISIT

A schedule of study evaluations is provided in [Appendix A](#).

All study visits should occur on the day scheduled  $\pm$  2 days.

### 12.1. Baseline/Week 0

Potential subjects for the study will be fully informed about the nature of the study and possible AEs. Subjects who wish to participate in the study must read and understand the consent form and sign the document after the investigator has answered all questions to the candidate's satisfaction. Further procedures can begin only after the consent form has been signed.

The Week 16 Visit of Study ADS-AMT-MS301 will serve as the Baseline/Week 0 study visit of Study ADS-AMT-MS303 for those subjects who consent to participate. Per the Schedule of Events in [Appendix A](#), procedures that are shared between Study ADS-AMT-MS301 (Week 16 Visit) and the Baseline/Week 0 visit of the present study do not need to be repeated and the data will be captured in both studies.

The following procedures will be performed to establish each subject's qualifications for enrollment into the study:

- The subject is fully informed about the study and gives written informed consent to participate in the study
- Review inclusion/exclusion criteria and evaluate initial subject eligibility
- Record demographic information
- Medical history with an emphasis on the subject's MS and walking impairment, and past treatments for these conditions; alcohol and drug use, other neurological diseases, psychiatric disorders including Major Depressive Disorder or symptom (eg, hallucinations, agitation, paranoia, suicidal ideation), history of seizures, stroke or transient ischemic attack (TIA); history of myocardial infarction (MI) or congestive heart failure (CHF); and history of cancer
- Record all medications currently taken
- Assess and record AEs
- Complete physical examination
- Obtain subject weight in kilograms
- Vital signs (blood pressure, respiratory rate, heart rate, and temperature)
- Blood sample for central laboratory analysis including hematology, serum chemistry, and eGFR
- Urinalysis

- Blood sample for serum pregnancy test in female subjects of childbearing potential
- MSWS-12, T25FW, TUG, and 2MWT assessments (Full details on how individual efficacy assessments are to be performed will be provided in the study manual. These assessments are to be done in this order.)
- Administer the C-SSRS (administration instructions and forms will be provided in the study manual)

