### 13.1.3. Adverse Event of Special Interest (AESI)

There are two AEs of special interest (AESIs) in this study:

- Hallucinations (including visual, auditory, or other sensory modality)
- Suicidality (including suicidal ideation and attempted suicide)

For either AESI, a specific AESI CRF page will be filled out at the time the investigator becomes aware of the event, including a brief narrative summary of the event.

Additional AESIs may also be identified by the Medical Monitor. Significant AEs of particular clinical importance, other than SAEs, AESIs pre-specified above, and those AEs leading to discontinuation of a subject from the study, may also be classified at or by study’s end as AESIs. For each such AESI, additional information may be requested from the investigator so that a brief narrative of the event may be written and included in the Clinical Study Report.

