## **13.2. Recording Adverse Events**

### **13.2.1. Adverse Event Recording**

Adverse events spontaneously reported by the subject and/or in response to an open question from the study personnel or revealed by observation will be recorded during the study at the investigational site. Any AE (ie, a new event or an exacerbation of a pre-existing condition) with an onset date after start of study drug administration up to and including the designated follow-up safety visit should be recorded as an AE on the CRF.

Information about all AEs, including SAEs, that occur after a subject has been enrolled and completed Study ADS-AMT-MS301, whether before treatment, during treatment, or within 14 days following the cessation of treatment must be recorded. AEs occurring after a subject has begun study drug (ADS-5102) in Study ADS-AMT-MS303 are designated as treatment-emergent adverse events (TEAEs) to distinguish these from AEs occurring after enrollment and completion of Study ADS-AMT-MS301 but before treatment in Study ADS-AMT-MS303.

All AEs must be recorded on the AE CRF regardless of the severity or relationship to study drug. It is important that investigators also report all AEs that result in permanent discontinuation of the study drug being studied, whether serious or non-serious.

Out of range clinical laboratory findings (eg, clinical chemistry, hematology) or findings on other assessments (eg, electrocardiogram, X-rays, vital signs) per se are not reported as AEs. However, if the out of range finding is deemed clinically significant or is associated with signs and/or symptoms, the finding must be recorded as an AE (and additionally as an SAE if it meets the criteria of being serious; see [Section 13.1.2](#)), as described above.

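### The C-SSRS is summarised only by means, mean changes and a graph, so the plan as supplied gives no count from the scale of subjects with suicidal ideation or behaviour

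*Combined protocol and SAP*

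**What the plan says.** Protocol section 14.6 gives one sentence on the analysis of the C-SSRS, and the synopsis repeats it: "Descriptive statistics for the mean and mean changes in the C-SSRS will be generated by study visit". A further sentence adds a graph. Neither place mentions a count, a percentage, a shift from Week 0, a subject listing or a breakdown by treatment sequence for this scale.

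Section 11.3 says that the C-SSRS "can provide valuable information as to the presence and intensity of suicidal ideation" and leaves the details of administration to the study manual. No numeric C-SSRS score is defined in the protocol. Appendix A schedules the scale at every clinic visit, including early termination (ET) and safety follow-up.

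Other safety data in section 14.6 are handled differently. Treatment-emergent adverse events (TEAEs) are reported as incidences by treatment sequence and overall. For the laboratory data, "The incidence of potentially clinically significant changes in laboratory parameters at each study visit will be tabulated", and vital signs are treated in the same way.

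Suicidality also has a separate reporting route. Section 13.1.3 names as one of two pre-specified adverse events of special interest (AESIs) "Suicidality (including suicidal ideation and attempted suicide"), and for these "a specific AESI CRF page will be filled out at the time the investigator becomes aware of the event".

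**The concern.** Safety and tolerability are the primary objective, suicidality is one of the two pre-specified AESIs, and the C-SSRS is the structured instrument used to look for it. The question a reader of the study report will ask is how many subjects had ideation or behaviour on treatment, and how many of those were new or worse than at Week 0. A mean over the whole cohort does not answer that when most subjects score nothing. In a mean change, subjects who improve also offset subjects who worsen. Since no score is defined, it is not stated what would be averaged.

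What is at stake is a count from the instrument given to all subjects on a common schedule, and a means of checking whether the AE and AESI pages picked up the subjects whom the scale identified.

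**Working it through.** The plan states no figure on this point, so there is nothing to reproduce. The check has two parts.

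**1. Can a count be recovered from the planned statistics?**

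Inputs: N = 540 is the protocol's approximate ceiling (sections 7.2 and 14.1). The integer changes below are assumptions for illustration, because the documents give no C-SSRS scoring. The widest reading of the planned summary borrows the list in section 14.5: "Descriptive statistics (ie, mean, standard error, median, minimum/maximum, 95% confidence intervals [CI] for the changes from baseline").

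Formulas: mean = S/N; SD² = (Q − S²/N)/(N − 1); SE = SD/√N. Here S is the sum of the changes and Q is the sum of their squares.

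| | Pattern A | Pattern B |
|---|---|---|
| Non-zero changes | 5, 3, 3 | 5, 4, 1, 1 |
| S | 11 | 11 |
| Q | 25 + 9 + 9 = 43 | 25 + 16 + 1 + 1 = 43 |
| Mean | 11/540 = 0.0204 | 0.0204 |
| SD | √[(43 − 121/540)/539] = 0.2817 | 0.2817 |
| SE | 0.2817/√540 = 0.0121 | 0.0121 |
| Median | 0 | 0 |
| Minimum, maximum | 0, 5 | 0, 5 |
| Subjects who worsened | 3 (0.56%) | 4 (0.74%) |

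The confidence interval is built from the mean and SE, so it is the same too. Every statistic in the section 14.5 list agrees, and the counts differ. This does not depend on N = 540: S and Q are equal in the two patterns, so the mean and SE agree at any N. At an assumed N of 270, for example, both means are 11/270 = 0.0407.

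Cancellation: if 2 subjects worsen by 5 and 2 others improve by 5, the mean change is (2 × 5 − 2 × 5)/540 = 0, the same as if nobody had changed.

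**2. Does another planned output supply the count?**

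- Section 13.1.3 makes suicidal ideation and attempted suicide AESIs, and section 13.2.3 requires an AESI to be entered on the AE page as well.
- Section 13.2.1 says that if a finding is clinically significant or "is associated with signs and/or symptoms, the finding must be recorded as an AE". Section 12.1 asks in the medical history for any psychiatric "symptom (eg, hallucinations, agitation, paranoia, suicidal ideation"), so the protocol itself treats ideation as a symptom.
- Section 14.6 then counts TEAEs by system organ class and preferred term. Most new cases should therefore be counted there.
- This route has limits. Section 13.1.1 has AEs elicited by a nonspecific question, and it excludes pre-existing conditions that do not worsen. Section 11.3 directs AE capture of new or worsening depression, but does not say that a positive C-SSRS must itself be entered as an AE. The list of AE tables in section 14.6 has no row for AESIs.

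The AE route thus gives a count of reported events. It does not give a count from the C-SSRS, and without one the two sources cannot be compared in the planned tables.

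**The case against.** The strongest reply is that suicidality is already counted. The AESI definition, the dedicated page and the TEAE tables cover new cases. Giving the C-SSRS at each clinic visit is itself a way for the investigator to become aware of one. What the AE route leaves out by design is ideation present before dosing in this study that does not get worse, which is not treatment-emergent. This largely stands, and it limits the point to the missing instrument-based count and the cross-check.

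Second, section 14.5 defers the details of all analyses to the SAP, which was not available for this review. A C-SSRS table may be there. This also stands. However, section 14.6 is not silent: it names means and mean changes, so the protocol wording would still need aligning.

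Third, the standard error carries information. Under the same assumptions, with minimum 0 and maximum 5, a mean of 0.0185 with an SE of 0.0131 fits only one pattern, two subjects changing by 5. So the count can sometimes be worked back, given enough decimals. The pair in the working shows that it cannot always be, and working back from rounded summaries is no substitute for reporting the count.

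A reader might infer that the study has no count of suicidality at all, or that C-SSRS counts have been left out of the study's analysis altogether. The documents support neither: the first overlooks the AE and AESI route, and the second cannot be judged without the SAP.

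**Conclusion.** The concern holds in a limited form and should be fixed. The stated C-SSRS summary does not report how many subjects had ideation or behaviour, and the full section 14.5 set of statistics does not determine that number. The gap is a missing count from the systematic instrument, and the check on AE and AESI capture that goes with it. It is not a total absence of suicidality reporting.

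The numerical example (3 against 4 subjects with identical statistics) rests on assumed integer scores and serves only to show that the count is not determined. It is not an estimate of what this trial will see. The documents give no expected frequency of ideation, so the practical size of the gap cannot be stated. Confidence is medium, because the SAP may already contain the table.

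**What to change.** In section 14.6 and the synopsis, replace or supplement the C-SSRS means with the number and percent of subjects with:

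- any post-baseline suicidal ideation;
- any post-baseline suicidal behaviour;
- new onset or worsening of either from Week 0.

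Include the ET visit in the post-baseline data, and present the results by treatment sequence and overall. If any mean is kept, state which score is averaged. Align the SAP, or confirm that it already does this.

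By-visit tables, a full shift table and a listing of positive cases are optional additions.

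Cost: one or two tables from data already collected, with matching wording in the protocol and SAP. No new assessment is needed.
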